#### **4.1.8.2 Presentation**

All concomitant medications and disallowed medications will be summarized separately in a descriptive manner, by presenting the number and percentage of subjects receiving the medication by ATC classification and generic drug name. Rescue treatments will be similarly summarized, the presentation including additional categories for dialysis initiation and change in dialysate K concentration.

#### **4.1.9 Study Drug Compliance**

##### **4.1.9.1 Definitions and Derivations**

Compliance will be derived from an estimate of the actual exposure (in grams of IP), obtained through sachet counts, and the planned exposure to IP as indicated by the investigator (also in grams of IP), from first planned dose date to last planned dose date, accounting for dose interruptions. No compliance will be derived for subjects who did not receive study treatment. The last planned dose for subjects who withdraw from the study or withdraw from the treatment is the date of respective withdrawal.

Compliance will be analysed as a continuous variable, as well as a categorical variable, with categories defined as <80%, 80% to 120% and >120%.

##### **4.1.9.2 Presentation**

Compliance during the study will be presented by means of descriptive summary statistics, as described in Section 3.3.

#### **4.1.10 Duration of follow-up**

##### **4.1.10.1 Definitions and Derivations**

**Time in study to SED (months)** is defined as:

$(\min(\text{withdrawal of consent, death, LTFU, SED}) \text{ date} - \text{randomization date} + 1) / 30.4$

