## 7.2 Participant Withdrawal from the Study

- A participant may withdraw consent from the study at any time at his/her own request without prejudice to further treatment. In exceptional circumstances, the participant may be withdrawn at any time at the discretion of the investigator for safety, behavioral, compliance, or administrative reasons.
- A participant who considers withdrawing consent from the study must be informed by the investigator about modified follow-up options (eg, telephone contact, a contact with a relative or treating physician, or information from medical records). Participant Follow-Up Checklist Form and Withdrawal of Consent Checklist should be used to document the process.
- At the time of withdrawal from the study, if possible and agreed by the patient, a PIDV should be conducted at the earliest possible dialysis visit after the last dose of study intervention; refer to Section 7.1.4 and the SoA (Section 1.3) for data to be collected at the time of study withdrawal. A follow-up visit should be performed 14 days ( $\pm$  7 days) after last dose of the study intervention/ PIDV if agreed by the patient. This visit will be considered SCV. Date of SCV, if performed, will be considered date of withdrawal of consent.
  - If the patient does not agree to have PIDV, follow-up visit/ SCV performed, it will not be performed, and the date of participant's consent withdrawal will be documented by the Investigator in the source data and EDC.
- At the time of withdrawal of consent from the study, if possible, a PIDV should be conducted at the earliest possible dialysis visit after the last dose of study intervention; refer to Section 7.1.4 and the SoA (Section 1.3) for data to be collected at the time of study withdrawal and follow-up and for any further evaluations that need to be completed. The SCV should be performed 14 days ( $\pm$  7 days) after the participant's PIDV.
  - The participant will discontinue the study intervention and be withdrawn from the study at that time.

- If the participant withdraws consent for disclosure of future information, the sponsor may retain and continue to use any data collected before such a withdrawal of consent.

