### **7.3        Lost to Follow-up**

The term lost to follow-up will be limited to only participants with unknown vital status at study end (if not dead, participants need to have a date last known alive after randomization).

The following actions must be taken if a participant fails to return to the clinic for a required study visit:

- The site must attempt to contact the participant and reschedule the missed visit as soon as possible and counsel the participant on the importance of maintaining the assigned visit schedule and ascertain whether the participant wishes to and/or should continue in the study.
- Before a participant is deemed lost to follow-up, the investigator or designee must make every effort to regain contact with the participant (where possible, 3 telephone calls and, if necessary, a certified letter to the participant's last known mailing address or local equivalent methods). These contact attempts should be documented in the participant's medical record.
- Efforts to reach the participant should continue until the end of the study
- Site personnel, or an independent third party, will attempt to collect the vital status of the participant within legal and ethical boundaries for all participants randomized, including those who did not get study intervention. Public sources may be searched for vital status information. If vital status is determined, this will be documented, and the participant will not be considered lost to follow-up. Sponsor personnel will not be involved in any attempts to collect vital status information.

Discontinuation of specific sites or of the study as a whole are handled as part of [Appendix A](#).

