#### **3.4.1.2 Withdrawal of consent (WoC)**

Withdrawal of consent (WoC) refers to the date when the patient withdrew their consent for participation in the study.

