#### **3.4.1.3 Lost to follow-up (LTFU)**

Lost to follow-up (LTFU) refers to the last date of contact with the patient if the contact with the patient was lost during the course of the study.

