**Table 1 Summary of endpoints, intercurrent event strategy, and population level summary for the primary objective**

Purpose	Endpoint	Intercurrent event strategy and censoring rules	Population level summary
Primary objective: To evaluate the efficacy of SJC compared with placebo in reducing the time event of the primary composite endpoint of SCD, all stroke, or hospitalization/intervention/ED visit due to arrhythmias			
Establishing the efficacy of treatment with regards to risk for the occurrence of the primary endpoint events	Time to first occurrence of SCD, stroke, or hospitalization /intervention /ED visit due to arrhythmias (atrial fibrillation [AF], bradycardia, asystole, ventricular tachyarrhythmias [such as VF, VT, etc])	Events included in analysis regardless of treatment discontinuation and additional therapy (treatment policy).  Patients censored at the earliest of death that is non-SCD, WoC, LTFU, study discontinuation for other reason, and SED.	Hazard Ratio (SJC/placebo)
Sensitivity analyses of primary analysis. Details in Section 4.2.1.5			
Sensitivity to classification of cause of death	Time to the first occurrence of SCD or death adjudicated as undetermined, stroke, or hospitalization /intervention /ED visit due to arrhythmias (atrial fibrillation [AF], bradycardia, asystole, ventricular tachyarrhythmias [VT]).	Events included in analysis regardless of treatment discontinuation and additional therapy (treatment policy).  Patients censored at the earliest of death that is non-SCD and has a known cause, WoC, LTFU, study discontinuation for other reason, and SED.	Hazard Ratio (SJC/placebo)
Sensitivity to inclusion of post-SED events	Time to first occurrence of a primary endpoint event	Events included in analysis regardless of treatment discontinuation and additional therapy (treatment policy).  Patients not censored at SED. All other censoring rules used in the main analysis apply.	Hazard Ratio (SJC/placebo)
Supplementary analyses-of the primary objective. Details in Section 4.2.1.6			

Purpose	Endpoint	Intercurrent event strategy and censoring rules	Population level summary

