Impact of non-SCD as a component in the primary endpoint composite	Time to first occurrence of all cause death, stroke, or hospitalization /intervention /ED visit due to arrhythmias (atrial fibrillation [AF], bradycardia, asystole, ventricular tachyarrhythmias [VT])	Events included in analysis regardless of treatment discontinuation and additional therapy (treatment policy).  Patients censored at the earliest of WoC, LTFU, study discontinuation for other reason, and SED.	Hazard Ratio (SZC/placebo)
Impact of drop-in (patients starting treatment with non-protocolized SZC during study)	Time to first occurrence of a primary endpoint event	Events occurring post “drop-in” excluded from the analysis (while not on non-protocolised SZC).  Patients censored at the earliest of non-SCD, WoC, LTFU, study discontinuation for other reason, SED and the time of initiation of non-protocolized SZC, if such occurs.	Hazard Ratio (SZC/placebo)

Further details can be found in Section 4.2.1

**Table 2 Summary of secondary endpoints, intercurrent event strategy, and population level summary for the secondary objectives (endpoints are listed in statistical testing order)**

Testing Order	Endpoint	Intercurrent event strategy and censoring rules	Population level summary
1	S-K of 4.0-5.5 mmol/L (yes/no) after the long interdialytic interval (LIDI) at the 12-month visit	Observations included in analysis regardless of treatment discontinuation and additional therapy (treatment policy)	Odds Ratio (SZC/placebo)
2	Time to first occurrence of hospitalization/intervention/ED visit due to arrhythmias (AF, bradycardia, asystole, ventricular tachyarrhythmias [such as VF, VT, etc]).	Observations included in analysis regardless of treatment discontinuation and additional therapy (treatment policy).  Patients censored at the earliest of death, WoC, LTFU, Other reasons of discontinuation and SED.	Hazard Ratio (SZC/placebo)

Testing Order	Endpoint	Intercurrent event strategy and censoring rules	Population level summary
3	Number of hospitalizations/interventions /ED visits due to arrhythmias (AF, bradycardia, asystole, or VT [such as VF, VT, etc])	Observations included in analysis regardless of treatment discontinuation and additional therapy (treatment policy)  Patients censored at the earliest of death, WoC, LTFU, Other reasons of discontinuation or SED.	Rate ratio (SZC/placebo)

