#### **4.2.2.2 Number of events analyses**

Two analyses aimed at examining the difference in the expected number of events of interest, per a unit of time, between treatment arms will be performed. In the first analysis, aimed at evaluating the corresponding secondary objective, the events of interest are hospitalizations /interventions /ED visits due to arrhythmias. Only arrhythmias events that are positively adjudicated will be considered. Multiple hospitalizations /interventions /ED visits due to a single positively adjudicated arrhythmias will be counted as one event. In the second analysis, aimed at evaluating the corresponding exploratory objective, the events of interest are use of rescue therapy for hyperkalemia.

For both of these endpoints, a negative binomial regression model with number of events as response and the same covariates as in the main analysis of the primary endpoint (Section 4.2.1.4) will be used. The logarithm of the subject's corresponding follow-up time will be used as an offset variable in the model to adjust for subjects having different follow-up times during which the events can occur. See Table 2 and 3 for the definition of the follow-up time (censoring).

The estimated event rate in the respective treatment arm, rate ratio between these, corresponding 95% confidence interval, and two-sided p-value will be presented. Total number of events that occurred up to the point of censoring will also be presented, by treatment group.

Time to event analysis for recurrent events may be conducted as a supplementary analysis.

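### The follow-up duration formula in SAP 4.1.10.1 leaves out study discontinuation for other reasons, so the descriptive follow-up summary can only be too long

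*SAP*

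**What the plan says.** SAP 4.1.10.1 defines *Time in study to SED*, in months, as the earliest of four dates ("withdrawal of consent, death, LTFU, SED") minus the randomization date, plus 1, divided by 30.4. SAP 4.1.10.2 summarizes this quantity descriptively and plots its empirical cumulative distribution by treatment group.

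The endpoint tables use a longer list. For the primary endpoint, SAP Table 1 says: "Patients censored at the earliest of death that is non-SCD, WoC, LTFU, study discontinuation for other reason, and SED". For the time to first arrhythmia-related hospitalization, intervention or ED visit, SAP Table 2 says: "Patients censored at the earliest of death, WoC, LTFU, Other reasons of discontinuation and SED". The other time-to-event and count rows of Tables 1 to 3 carry the same extra reason. For the negative binomial offset, SAP 4.2.2.2 directs: "See Table 2 and 3 for the definition of the follow-up time (censoring".

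Three definitions show who falls in the extra category:

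- Withdrawal of consent (SAP 3.4.1.2) "refers to the date when the patient withdrew their consent for participation in the study".
- Loss to follow-up (SAP 3.4.1.3) "refers to the last date of contact with the patient if the contact with the patient was lost". Protocol 7.3 is narrower: "The term lost to follow-up will be limited to only participants with unknown vital status at study end".
- Protocol 7.2 provides a separate exit, for exceptional cases: "the participant may be withdrawn at any time at the discretion of the investigator for safety, behavioral, compliance, or administrative reasons".

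**The concern.** The SAP contains two definitions of when follow-up ends, and they differ by one reason. A participant withdrawn by the investigator has not withdrawn consent. If vital status is known, that participant is not lost to follow-up under the protocol's definition either. If the participant is alive at the SED, the only date left in the minimum is the SED itself, and the formula counts months in which nothing was observed.

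What is at stake is the accuracy of the reported follow-up duration and its by-arm plot. In that display, this form of early exit looks like full follow-up. If such exits differed between arms, the plot would not show it.

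**Working it through.** No figure stated in the plan depends on this formula, so there is none to reproduce. The check compares the lists and then illustrates the size.

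**Step 1: the lists side by side.**

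| End of follow-up | SAP 4.1.10.1 | SAP Table 1, main analysis | SAP Table 2, count endpoint |
|---|---|---|---|
| Withdrawal of consent | yes | yes | yes |
| Death | any | non-SCD (SCD is an event) | any |
| Loss to follow-up | yes | yes | yes |
| Discontinuation for another reason | **no** | yes | yes |
| SED | yes | yes | yes |

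The count endpoint is the cleanest comparison, because its list is the 4.1.10.1 list plus the one missing term.

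**Step 2: can another term absorb the category?** Not under the definitions given. Consent withdrawal is the patient's own act, and loss to follow-up needs lost contact. The tables list the category beside those two, so they treat it as separate. SAP 3.4.1.4 has a period that ends at last contact or death, but it is defined for safety analyses only.

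**Step 3: direction.** Leaving a date out of a minimum can raise the result or leave it unchanged. It cannot lower it.

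- Alive at the SED: excess = SED − discontinuation date.
- Death before the SED found through the vital-status search: excess = death date − discontinuation date. This is smaller, but still too long.

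**Step 4: one participant.** Inputs: 37 months from randomization to SED (the anticipated average treatment period in SAP 3.3, used as a stand-in) and discontinuation at month 12. The formula gives 37 months and the observed time is 12, so the excess is 37 − 12 = 25 months. For a stop at month 6, 18.5 or 30, the excess is 31, 18.5 or 7 months.

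**Step 5: the mean.** The documents give no rate, so the share *d* is assumed, as is an average exit at mid-follow-up. Excess in the mean = *d* × 37/2 = *d* × 18.5 months. Patient-years for the planned 2800 participants = 2800 × *d* × 18.5/12.

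| Assumed share *d* | Participants | Excess in mean (months) | Share of 37 months | Patient-years |
|---|---|---|---|---|
| 0.5% | 14 | 0.005 × 18.5 = 0.09 | 0.25% | 22 |
| 1% | 28 | 0.01 × 18.5 = 0.19 | 0.5% | 43 |
| 2% | 56 | 0.02 × 18.5 = 0.37 | 1.0% | 86 |
| 5% | 140 | 0.05 × 18.5 = 0.93 | 2.5% | 216 |

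Under these assumptions the figures are upper values, because they ignore deaths before the SED, at which the formula does stop.

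**Step 6: reach.** SAP 4.2.1.2 takes the censoring rules for the primary analyses from Table 1. SAP 4.2.2.1 and 4.2.2.2 take theirs from Tables 2 and 3. None of them uses the 4.1.10.1 formula.

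**The case against.** The case against giving this weight is good on consequence, although it does not remove the difference between the lists.

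- **No inferential result moves.** A reader might infer that time at risk in the Cox models, or the negative binomial offset, is wrong. The documents do not support that, because those analyses follow Tables 1 to 3. Nor is a mismatch with Cox time evidence of error. Cox time stops at the first endpoint event while time in study runs on, so the two differ by design for every participant with a non-fatal primary event. This stands in full.
- **The participants are not hidden.** A reader might infer that this incomplete follow-up escapes notice. It does not. SAP 4.1.1.2 reports study completion with reasons for non-completion, and the number with complete primary-endpoint follow-up. SAP 4.2.1.3 and 4.2.4 report, by arm, those censored before the SED and why. This largely stands. Those outputs give counts and reasons, whereas lost time is shown only by the summary and plots of 4.1.10.2.
- **The group is probably small.** Protocol 7.2 reserves investigator withdrawal for exceptional cases. Protocol 7.1.4 keeps participants in follow-up after they stop study drug. Protocol Appendix A 9 allows transfer from closed sites. Protocol 7.2 also treats the closing visit after study withdrawal, if held, as the consent-withdrawal date. Read broadly, that could give some of these participants a date already in the formula. This stands, and it points to the low end of the assumed range.
- **The measure may be potential follow-up.** This fails. The formula already stops at consent withdrawal and at loss to follow-up, so it is meant to measure observed time, and the SAP gives no reason to treat one early exit differently.

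**Conclusion.** The omission is real and the formula is wrong as written, but the point is minor. Followed literally, SAP 4.1.10.1 overstates follow-up for anyone whose study participation ends for a reason other than consent withdrawal, loss to follow-up or death. The credit runs to the SED only for those alive then. For those found to have died earlier, it stops at death.

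The overstatement of the mean is about 0.19 months for each 1% of participants affected, so at most about 0.09 to 0.93 months for shares of 0.5% to 5%. This rests on three assumptions: the share, which the documents do not give; exit on average at mid-follow-up; and 37 months of average treatment as a stand-in for time from randomization to SED. Hazard ratios, rate ratios, p-values, alpha and power are unaffected.

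**What to change.** Add the date of study discontinuation for other reasons to the minimum in SAP 4.1.10.1, so that it stops at the same early-exit reasons as SAP Tables 1 to 3 and the follow-up time used in SAP 4.2.2.2.

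The cost is one term in a derivation. The date is already needed to censor the primary endpoint, so no new data are required, and neither the protocol nor any model changes. Reported follow-up may become slightly shorter.

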##### **4.1.10.2 Presentation**

Duration of follow-up as described above will be summarized using descriptive statistics, as a continuous variable. Empirical Cumulative Distribution Function (eCDF) plots will also be produced, by treatment group.

#### **4.1.11 Exposure**

##### **4.1.11.1 Definitions and Derivations**

The duration of total planned exposure (months) to study drug is defined as the length of period on study drug, calculated for each subject as (date of last actual dose – date of first planned dose +1)/30.4.

The duration of planned exposure excluding interruptions (months) to study drug is defined as total planned exposure (months) minus total interruptions. Interruptions will be identified from eCRF EX module. Similarly, duration of exposure to a particular dose will be defined as the time the dose was prescribed to the date it was dose stop plus one day.

#### **4.1.11.2 Presentation**

Duration of exposure and exposure excluding interruptions will be summarized using descriptive statistics as described in Section 3.3 by treatment group. Duration of exposure to a particular dose level will be summarized in a similar manner, by treatment group and dose level.

Number of subjects (%) with any treatment interruption, as well as reasons for interruption, will be summarized descriptively based on the SS data set for each treatment group.

A figure with number of subjects on study drug vs days from randomisation will be produced.

A plot of the proportion of subjects on each dose (including dose 0) over time will be produced by treatment group. This will be complimented by a table summarizing the average doses the subjects receive during the course of the study, as well as a one presenting the proportions of time a subject spends on each dose level.

A listing of subjects by batch number of study medication and dosage over time will be generated.

## **4.2 Endpoint Analyses**

This section covers details related to endpoints, intercurrent event strategies, handling of missing data and analyses pre-specified for the efficacy objectives. All defined analyses will be performed using FAS if not otherwise stated. This implies that the population to which the results are generalizable is the population of all subjects that satisfy inclusion and exclusion criteria. For all analyses, the treatments, or, in terms of estimands, “treatment conditions”, will be SZC or Placebo administrated according to the dosing regimen, as detailed in CSP Section 6.1.2.

Unless otherwise specified, for all analyses for which a statistical test is performed, the null hypothesis corresponds to no difference between SZC and Placebo treatment arms.

The unit of time for all time to event analysis will be days.

Endpoints, intercurrent event strategies and censoring rules, as well as population level summaries, are given in [Table 1](#) for primary objective, [Table 2](#) for secondary objectives, and [Table 3](#) for exploratory objectives.

**Table 1 Summary of endpoints, intercurrent event strategy, and population level summary for the primary objective**

Purpose	Endpoint	Intercurrent event strategy and censoring rules	Population level summary
Primary objective: To evaluate the efficacy of SJC compared with placebo in reducing the time event of the primary composite endpoint of SCD, all stroke, or hospitalization/intervention/ED visit due to arrhythmias			
Establishing the efficacy of treatment with regards to risk for the occurrence of the primary endpoint events	Time to first occurrence of SCD, stroke, or hospitalization /intervention /ED visit due to arrhythmias (atrial fibrillation [AF], bradycardia, asystole, ventricular tachyarrhythmias [such as VF, VT, etc])	Events included in analysis regardless of treatment discontinuation and additional therapy (treatment policy).  Patients censored at the earliest of death that is non-SCD, WoC, LTFU, study discontinuation for other reason, and SED.	Hazard Ratio (SJC/placebo)
Sensitivity analyses of primary analysis. Details in Section 4.2.1.5			
Sensitivity to classification of cause of death	Time to the first occurrence of SCD or death adjudicated as undetermined, stroke, or hospitalization /intervention /ED visit due to arrhythmias (atrial fibrillation [AF], bradycardia, asystole, ventricular tachyarrhythmias [VT]).	Events included in analysis regardless of treatment discontinuation and additional therapy (treatment policy).  Patients censored at the earliest of death that is non-SCD and has a known cause, WoC, LTFU, study discontinuation for other reason, and SED.	Hazard Ratio (SJC/placebo)
Sensitivity to inclusion of post-SED events	Time to first occurrence of a primary endpoint event	Events included in analysis regardless of treatment discontinuation and additional therapy (treatment policy).  Patients not censored at SED. All other censoring rules used in the main analysis apply.	Hazard Ratio (SJC/placebo)
Supplementary analyses-of the primary objective. Details in Section 4.2.1.6			

Purpose	Endpoint	Intercurrent event strategy and censoring rules	Population level summary
Impact of non-SCD as a component in the primary endpoint composite	Time to first occurrence of all cause death, stroke, or hospitalization /intervention /ED visit due to arrhythmias (atrial fibrillation [AF], bradycardia, asystole, ventricular tachyarrhythmias [VT])	Events included in analysis regardless of treatment discontinuation and additional therapy (treatment policy).  Patients censored at the earliest of WoC, LTFU, study discontinuation for other reason, and SED.	Hazard Ratio (SZC/placebo)
Impact of drop-in (patients starting treatment with non-protocolized SZC during study)	Time to first occurrence of a primary endpoint event	Events occurring post “drop-in” excluded from the analysis (while not on non-protocolised SZC).  Patients censored at the earliest of non-SCD, WoC, LTFU, study discontinuation for other reason, SED and the time of initiation of non-protocolized SZC, if such occurs.	Hazard Ratio (SZC/placebo)

Further details can be found in Section 4.2.1

**Table 2 Summary of secondary endpoints, intercurrent event strategy, and population level summary for the secondary objectives (endpoints are listed in statistical testing order)**

Testing Order	Endpoint	Intercurrent event strategy and censoring rules	Population level summary
1	S-K of 4.0-5.5 mmol/L (yes/no) after the long interdialytic interval (LIDI) at the 12-month visit	Observations included in analysis regardless of treatment discontinuation and additional therapy (treatment policy)	Odds Ratio (SZC/placebo)
2	Time to first occurrence of hospitalization/intervention/ED visit due to arrhythmias (AF, bradycardia, asystole, ventricular tachyarrhythmias [such as VF, VT, etc]).	Observations included in analysis regardless of treatment discontinuation and additional therapy (treatment policy).  Patients censored at the earliest of death, WoC, LTFU, Other reasons of discontinuation and SED.	Hazard Ratio (SZC/placebo)

Testing Order	Endpoint	Intercurrent event strategy and censoring rules	Population level summary
3	Number of hospitalizations/interventions /ED visits due to arrhythmias (AF, bradycardia, asystole, or VT [such as VF, VT, etc])	Observations included in analysis regardless of treatment discontinuation and additional therapy (treatment policy)  Patients censored at the earliest of death, WoC, LTFU, Other reasons of discontinuation or SED.	Rate ratio (SZC/placebo)
4	Time to first instance of rescue therapy use for hyperkalemia	Observations included in analysis regardless of treatment discontinuation and additional therapy (treatment policy).  Patients censored at the earliest of death, WoC, LTFU, Other reasons of discontinuation and SED	Hazard Ratio (SZC/placebo)
5	S-K > 6.5 mmol/L (yes/no) after the LIDI at the 12-month visit	Observations included in analysis regardless of treatment discontinuation and additional therapy (treatment policy)	Odds Ratio (SZC/placebo)
6	Time to SCD	Observations included in analysis regardless of treatment discontinuation and additional therapy (treatment policy).  Patients censored at the earliest of non-SCD, WoC, LTFU, Other reasons of discontinuation and SED	Hazard Ratio (SZC/placebo)
7	Time to first occurrence of stroke	Observations included in analysis regardless of treatment discontinuation and additional therapy (treatment policy),  Patients censored at the earliest of death, WoC, LTFU, Other reasons of discontinuation and SED	Hazard Ratio (SZC/placebo)
8	Time to CV death	Observations included in analysis regardless of treatment discontinuation and additional therapy (treatment policy),  Patients censored at the earliest of non-CV death, WoC, LTFU, Other reasons of discontinuation and SED	Hazard Ratio (SZC/placebo)
9	Time to death of any cause	Observations included in analysis regardless of treatment discontinuation and additional therapy (treatment policy),  Patients censored at the earliest of WoC, LTFU, Other reasons of discontinuation and SED	Hazard Ratio (SZC/placebo)

